3.1.1. Premedication	12
3.1.2. Interventions	13
4. PARTICIPANT ENTRY	13
4.1 INCLUSION CRITERIA	13
4.2 EXCLUSION CRITERIA	13
4.3 WITHDRAWAL CRITERIA	14
5. ADVERSE EVENTS	14
5.1 DEFINITIONS	14
5.3 REPORTING PROCEDURES	14
6. ASSESSMENT AND FOLLOW-UP	15
7.1 SAMPLE SIZE	15
7.2 RECRUITMENT	15
7.3 FOLLOW-UP	16
7.4 DATA ANALYSIS	16
7.4.1. Data Collection	16
7.4.2. Data Management	16
7.4.3. Statistical analysis	16
8. REGULATORY ISSUES	16
8.1 ETHICS APPROVAL	16
8.2 CONSENT	17
8.3 CONFIDENTIALITY	17
8.4 INDEMNITY	17
8.5 SPONSOR	17
8.6 FUNDING	17
8.7 AUDITS	17
9. STUDY MANAGEMENT	17

10. PUBLICATION POLICY	17
APPENDIX 1. PARTICIPANT TIMELINE	18

GLOSSARY OF ABBREVIATIONS

DTC – Diurnal Tension Curve

GCC – Ganglion Cell Complex

IOP – Intraocular Pressure

MD – Mean Deviation

mDTC – modified Diurnal Tension Curve

NFL – Nerve Fiber Layer

NTG – Normal Tension Glaucoma

OCT – Optical Coherence Tomography

VF – Visual Field

WDT – Water Drinking Test

[figure not shown]
KEYWORDS

Intraocular pressure, stress test, correlation, water drinking test, modified diurnal tension curve, glaucoma progression, OCT, VF, normal tension glaucoma

STUDY SUMMARY

TITLE	The Water Drinking Test (WDT) in Glaucoma Study: WIGS
DESIGN	Observational cohort study
AIMS	To investigate the correlation and agreement between the intraocular pressure peaks detected during the water drinking test and modified diurnal tension curve in glaucomatous eyes and to analyse whether this is associated with prognostic outcome. We will also measure autonomic nervous system activation during the test to investigate one possible mechanism behind it.
OUTCOME MEASURES	Peak IOP measurements from the two different methods
POPULATION	Primary open-angle and normal tension glaucoma patients
ELIGIBILITY	Primary open-angle and normal tension glaucoma patients, not on anti-ocular hypertensive therapy.
	
- Able to give informed consent to participate in the study- Aged between 18 and 80 years of age- Clear optical media- Spherical equivalent +10D
DURATION	Single visit

REFERENCE DIAGRAM

1. INTRODUCTION

1.1 BACKGROUND

1.1.1. IOP and glaucoma

Glaucoma is a progressive optic neuropathy characterised by progressive loss of retinal ganglion cells, leading to thinning of the retinal nerve fibre layer and visual field loss^[1]. It is the leading cause of irreversible blindness in the world^[2] and affects more than 70 million people worldwide^[3].

Intraocular pressure (IOP) is the main risk factor for the development and progression of glaucoma^{[4] [5]}. The gold standard for intraocular pressure (IOP) measurement is applanation tonometry^[6]. Routine office measurements may not detect IOP peaks in roughly 30% of patients due to variation throughout the day^[7], and this detection failure may be responsible for visual field progression in apparently well-controlled patients^[5].

1.1.2. IOP measurement methods

To provide more reliable data, twenty-four hour diurnal tension curves (DTC) can be measured. However, 24-hour IOP monitoring is unfeasible and time consuming in the majority of circumstances. The modified diurnal tension curve (mDTC) involving IOP measurements every 2 or 3 hours during office hours is therefore often used as a shorter alternative.

The water drinking test (WDT) is a tool that aims to indirectly evaluate the eye's aqueous humor outflow facility^{[8] [9]} by putting the drainage system under 'stress' in a test similar to that which may be used in cardiology or endocrinology. More recent research has suggested that water overload with the WDT may correlate well with the IOP peaks detected during a 24-hour intraocular pressure measure^[10].

It remains unclear as to the physiological mechanism behind this observed IOP rise. Several hypotheses exist including increases in outflow resistance^[11], episcleral venous pressure^[12], choroidal expansion^[13] and change in blood osmolality. However, it has been observed in one study that 20% of subjects developed change in IOP before change in osmolality could be detected.

Centrally mediated causes, possibly triggered by gastric expansion have been postulated with regards to activation of the autonomic nervous system^[14], but this has mainly been characterised in terms of cardiovascular physiology as oppose to intraocular pressure rise. Some evidence has been published to suggest the time course of the autonomic changes observed (rise in blood pressure, reduction in heart rate) are not consistent with reflex activity^[15], however in this study only 500mls of water was ingested over 3-4 minutes. This aspect of the test requires further characterisation in relation to the time profiles of the IOP rise.

1.1.3. The role of the WDT in glaucoma

The WDT has been described as an independent risk factor for the development and progression of a glaucomatous field defect in patients with OAG^[9,16]. In a prospective study of 5000 patients with open angle glaucoma, the authors found five potential risk factors for the development of glaucomatous visual field lesion: outflow facility, age, IOP, cup/disk ratio

and change in IOP after water ingestion^[17]. These data have changed the concept of the WDT, which is now used as a useful tool to assess IOP peaks. Furthermore, the WDT is a reproducible^[18,19] low-cost and feasible test in the clinical practice.

1.1.4. OCT and glaucoma progression

[figure not shown]
OCT has been widely used to measure the thickness of the NFL and GCC, which have strong correlation with glaucoma disease stages^[20]. OCT can assist in the diagnosis of glaucoma to a certain extent, with faster rates of OCT progression associated with a higher risk of VF progression^[21]. OCT is thought to be more sensitive than VF in detecting progression in the earlier stages of the disease, hence the term 'pre-perimetric glaucoma'^[22]. Since OCT measurements have good repeatability and reproducibility,^[23] it is clinically advantageous to monitor glaucoma progression using objective OCT structural measurements in the early stages prior to visual field defects appearing.

1.1.5. Safety

The water drinking test (WDT) is a safe test for the majority of the population since its intervention is drinking water. However, there are individual cases where it may be harmful; any person with contra-indication of drinking large amounts of water in a small amount of time should be excluded. This includes patients with heart or kidney failure, or those with swallowing difficulties associated with neurological disorders or gastrointestinal strictures or stasis.

1.1.6. Previous studies

Previous studies have shown correlation between the water drinking test and the modified diurnal tension curve^[24]. Vasconcelos-Moraes CG et al.^[24] showed that the WDT peak was significantly correlated with the mDTC peak (Person's Correlation Coefficient $r=0.780$ for a 95% confidence interval between 0.716 to 0.831, $p<0.0001$), however this has not yet been widely reproduced. However, this study was conducted on POAG patients who were on topical therapy for raised intraocular pressure, and therefore were required to undergo a washout period of no medication.

Figure 2

Correlation between IOP peaks during the WDT and mDTC

This study showed 95% limits of agreement between the WDT and mDTC IOP peaks ranging from -3.9 mmHg to 8.2 mmHg. In 52.5% of the tests, the agreement was within ± 2 mmHg.

[figure not shown]

Figure 3

Agreement between the WDT and mDTC peaks

Eighty-two percent of eyes showed higher IOP peaks during the WDT than the mDTC (95% confidence interval between 0.0 and 6.99 mmHg).

When analysing glaucomatous progression De Moraes *et al.*^[9] showed that higher IOP peaks during the WDT were predictive of future visual field progression (hazard ratio=1.11; 95% confidence interval, 1.02 to 1.21; P=0.013), but also that the average and peak IOP during office hours over the same follow-up period were not significantly associated with progression (P=0.651 and 0.569, respectively). This study showed that IOP peaks detected with the WDT were predictive of future visual field progression in a treated POAG population, while office hours measures were not.

Another study performed by Yoshikawa *et al.*^[16] in normal tension glaucoma patients showed that the maximum IOP levels after the water drinking test in patients with progressive visual field loss was significantly greater than the levels observed for the non-progressive group. Given that a common indication for referring patients for the mDTC is disease progression despite normal pressures off-treatment ('normal-tension glaucoma'), the agreement of the two tests in this specific cohort is currently under-documented.

1.2 RATIONALE FOR CURRENT STUDY

The current method of using the mDTC is time consuming, labour intensive, and incomprehensive. Not only does the WDT have the potential to improve upon the time consuming and labour intensive nature of the test, but given the active element may improve diagnostic pickup and sensitivity for disease progression, given that the mDTC is only feasibly conducted during office hours.

Further work comparing the currently used mDTC and the WDT to assess IOP peak and fluctuation is necessary. The study mentioned above^[24] showed strong evidence of the clinical applicability of the WDT and its correlation with the mDTC. Furthermore, the IOP peak obtained by the WDT has been proved to be an independent risk factor for the development and progression of glaucoma^[5,8]. However, to date, there are no studies focusing on OCT data that will indicate progression of 'pre-perimetric' glaucoma, or any studies focusing on the most commonly referred group of patients referred for the test. This will aid us to discern the best way to assess IOP peaks and manage glaucoma treatment and progression.

Our hypotheses are:

- The peak IOP during the WDT correlates with mDCT
- Peak IOP during the WDT is associated with rate of glaucoma progression as measured with OCT
- Changes in autonomic variables associated with IOP rise are consistent with a autonomic reflex as the physiological mechanism behind the test.

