2. STUDY OBJECTIVES

- **Primary research objective** is to investigate the correlation and agreement between the intraocular pressure peaks detected during the water drinking test and the standard phasing test.

Secondary research objective is to correlate the IOPs obtained with both tests and prognostic outcome of the patients enrolled in the study to see whether these methods have predictive value for glaucoma progression. We will also measure autonomic nervous system activation (pupil size, heart rate and postural BP) during the test to investigate one possible mechanism behind it.

Lay summary

Raised intraocular pressure (IOP) is the main risk factor for the development and progression of glaucoma. The mDTC is a test that consists of four to five eye pressure measurements taken throughout office hours to check for rises in pressure that may be missed during their clinic appointment. To better try to assess the IOP peaks in a more time-efficient way, the water-drinking test has been developed. This involves the patient drinking a weight-adjusted volume of water within 5 minutes which has the effect of testing the ability to cope with increased demand for fluid to leave the eye. It is unclear as to the physiological mechanism by which this occurs. In this study we aim to compare the eye pressure measurements with both tests, and to see if either have any bearing on whether the patient's disease is getting worse. We also aim to show the changes in blood pressure and heart rate throughout the test.

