3.1.2. Interventions

Baseline and qualification assessments will take place on the day of the study. These include a medical, ophthalmic and drug history, ophthalmic examination, postural blood pressure measurement, testing of visual acuity, OCT/OCTA of the optic disc and macula and then IOP assessment. All ophthalmic assessments will be done on both eyes using the Heidelberg Spectralis® imaging system. The mDTC will be conducted as part of patient's regular visit and is standard of care which consists of 5 IOP measurements beginning at 8am and 2 hourly afterwards (+/- 15min). Following completion of mDTC patients will have their WDT as detailed below.

The water drinking test will occur following the mDTC and will involve the patient drinking 800mL of water at room temperature, within a maximum of five minutes, after a period of no fluid intake of at least 2 hours. This will come after a period of no fluid intake of at least 2 hours (2pm onwards). For the WDT, the first IOP measure will correspond to the last mDTC measure, and three IOP measurements will be made after water intake with a 15-minute interval between each. IOP measurements will be recorded using Goldmann Applanation Tonometry (GAT). At each 15 minute interval, postural blood pressure, heart rate, oxygen saturations and pupil diameter will be measured. The ambient light conditions will be monitored with a light meter. Imaging will then be repeated after one hour of the test.

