7.4.3 Statistical analysis

No interim analyses will take place as part of this pilot study. Data will be acquired using integrated Heidelberg® software packaged with the Heidelberg® Spectralis OCT system. Data for this initial pilot study will be collected using Microsoft® Excel, and analysed using R and GraphPad prism to compare IOPs between the mDCT and WDT.

Specific analyses will include:

- Generation of baseline data including mean and standard deviation of baseline characteristics
- Bland-Altman agreement analysis of the primary outcome
- Correlation analysis between WDT and rate of progression.
- Analysis of change in OCT measurements
- Change over time analysis for secondary outcomes compared to baseline

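### The listed WDT–progression correlation answers hypothesis 2 as worded, but cannot show that the water adds anything to ordinary pressure

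*Combined protocol and SAP*

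**What the plan says.** Section 1.2 gives hypothesis 2 as "Peak IOP during the WDT is associated with rate of glaucoma progression as measured with OCT". The exposure is the absolute peak, not the rise after the water. For this hypothesis section 7.4.3 lists "Correlation analysis between WDT and rate of progression" and names no covariate, adjusted model or rise-from-baseline measure. The secondary objective in section 2 is wider: to "correlate the IOPs obtained with both tests and prognostic outcome of the patients enrolled in the study". That implies a correlation for the mDTC as well, although 7.4.3 does not list one.

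Four other places bear on how the result will be read:

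- Section 1.2 argues that, because of its active element, the WDT "may improve diagnostic pickup and sensitivity for disease progression", the contrast being with the mDTC.
- Section 1.1.3 cites a large prospective study in which IOP "and change in IOP after water ingestion" appear as separate risk factors.
- Section 1.1.6 reports from an earlier study that "the WDT peak was significantly correlated with the mDTC peak", with r=0.780 (95% CI 0.716 to 0.831).
- Section 3.1.2 says that for the WDT "the first IOP measure will correspond to the last mDTC measure", so the two series share a reading.

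**The concern.** The WDT peak is the pressure before the water plus whatever the water adds. If ordinary pressure is related to progression, the WDT peak will tend to correlate with progression even when the response to water carries no information. A bare correlation cannot tell these two situations apart.

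Setting a correlation for the mDTC beside it does not help. One significant and one non-significant coefficient are not a test of the difference between them, nor of what one measure adds to the other. Section 1.1.6 shows how easily such a contrast is drawn: it places a significant WDT result (P=0.013) next to non-significant office-hours results (P=0.651 and 0.569) and presents the WDT as predictive where office measurements were not.

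At stake is the conclusion on the secondary objective. The study could report that the WDT predicts progression, and readers could credit the water when ordinary pressure did all the work.

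**Working it through.** The plan has no figure of its own for this analysis. The calculation in section 7.1 concerns a 2 mmHg difference in IOP peak, not a correlation with progression.

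**Inputs.** r(WDT peak, mDTC peak) = 0.78, CI 0.716 to 0.831 (section 1.1.6). n = 40 (section 7.1). Two-sided 5% test (assumed; sidedness is not stated). The correlation rho between mDTC peak and progression is not in the documents, so it is taken over a range from 0 to 0.6, with faster loss scored as higher.

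**Step 1: shared information.** 0.78² = 0.61, so the two peaks share 61% of their variance.

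**Step 2: expected correlation when the water adds nothing.** If the WDT peak is related to progression only through the mDTC peak, r(WDT, progression) = 0.78 × rho.

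**Step 3: how often that is significant.** By Fisher's z with n = 40, the probability is Φ(atanh(r)·√37 − 1.96) + Φ(−atanh(r)·√37 − 1.96). For rho = 0.4: r = 0.312, atanh(r) = 0.323, times 6.083 gives 1.963, and Φ(0.003) = 0.50.

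| Assumed rho | Expected bare r | Bare correlation significant |
|---|---|---|
| 0 | 0 | 5% |
| 0.1 | 0.08 | 8% |
| 0.2 | 0.16 | 16% |
| 0.3 | 0.23 | 31% |
| 0.4 | 0.31 | 50% |
| 0.5 | 0.39 | 71% |
| 0.6 | 0.47 | 87% |

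Simulation of 20,000 studies per setting agrees to within about two percentage points (31%, 52%, 71% and 88% for rho 0.3 to 0.6). In the same simulations the partial correlation given the mDTC peak was significant in about 5% throughout. Over the CI for the peak–peak correlation, with rho = 0.4, the simulated bare rate runs from 44% to 56%.

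**Step 4: which mDTC summary to adjust for.** A second simulation built the individual readings. Assumed SDs were 3 mmHg for the patient's level, 1.5 for a single reading and 2.5 for the rise, with the rise unrelated to level or progression. Here rho is the correlation of the true level with progression. The bare rate varies with how the rise is modelled over time.

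| Analysis | rho 0.4 | rho 0.5 |
|---|---|---|
| Bare correlation | 47% to 52% | 66% to 74% |
| Adjusted for mean of five mDTC readings | 5% | 5% |
| Adjusted for the single pre-water reading | 8% | 11% |

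Adjusting for the mDTC peak gave about 5% to 6%. The single reading does worse because its measurement error leaves residual confounding.

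**Step 5: cost in precision.** The variance inflation is 1/(1 − 0.78²) = 2.55, so the standard error grows by √2.55 = 1.60. This uses the peak–peak correlation; the documents do not give the correlation of the WDT peak with the mDTC mean. At n = 40, 80% power needs a bare r of tanh(2.80/√37) = 0.43 or a partial r of tanh(2.80/√36) = 0.44.

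**The case against.** The strongest reply is that the planned test matches the stated hypothesis. Hypothesis 2 is about association, and the objective in section 2 is to correlate pressures from both tests with outcome. If pressure level drives progression, a positive WDT correlation is a correct answer to both. This stands: the percentages above are not false-positive rates for hypothesis 2. They say how often a significant result would appear with no added value from the water.

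Second, added value is neither a hypothesis nor an objective. It rests on a hedged sentence in the rationale, and section 1.2 also offers the WDT as a quicker and less laborious test, for which similar marginal prediction would be informative. This stands too, and is why the correlation should stay. But the sentence is there, and the listed analysis cannot bear on it.

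Third, a reader might infer that the correlation is bound to come out positive. The documents do not support that. It depends on ordinary pressure predicting progression in this cohort. Section 1.1.1 names IOP as the main risk factor, but the treated cohort in section 1.1.6 showed no significant association for office-hours mean or peak. That cohort was treated and judged on visual fields, whereas the study summary here specifies untreated patients, so it does not settle the matter; it is the reason the range starts at zero. Even at rho = 0.3 the bare test is non-significant in 69% of studies.

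Fourth, 40 is a ceiling. Access to follow-up data is optional (section 6), which can only lower the significance rates. Section 8.2 leaves clinicians free to change treatment, which could weaken the link between pressure and progression.

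Finally, 7.4.3 describes what the analyses will include, so it does not exclude adjustment. It does not prespecify it either.

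**Conclusion.** The point holds as a gap between the analysis and the use the rationale suggests for it. The listed correlation tests hypothesis 2 as written. It cannot show that the water improves on the mDTC for progression, and nor can a pair of bare correlations. With no added value from the water, the bare test would be significant at n = 40 in about 5% of studies if ordinary pressure is unrelated to progression, rising to about 87% at an assumed rho of 0.6. Adjustment for mDTC pressure holds this at about 5% across that range.

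The size therefore rests on the cited 0.78 applying to this cohort and on a rho that the documents do not supply. It would be tempting to conclude that the adjusted coefficient should replace the correlation as the test of hypothesis 2. The documents do not support that, because it would substitute a different hypothesis. This is an inexpensive improvement to a secondary question in a self-described pilot that was not sized for it.

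**What to change.** In section 7.4.3:

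- Keep the correlation of the WDT peak with rate of progression as the test of hypothesis 2.
- Add a prespecified exploratory linear regression of OCT progression rate on the mean of the five mDTC readings plus the WDT peak, reporting the WDT coefficient with its 95% CI.
- State that any claim that the WDT adds to, or improves on, the mDTC for progression will rest on that coefficient and not on the bare correlation or correlations.

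This needs a few sentences and no new data, visits or patients. It should be settled before the 18-month outcomes are analysed.

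The cost is precision, as in step 5, made worse if fewer than 40 patients allow access to their data. In a simulation with the step 4 SDs, a mean rise of 3 mmHg and standardised effects of 0.3 each for level and rise (all assumed), the adjusted test found the real water effect in about 42% of studies; the bare test was significant in about 73%. A null adjusted result must therefore be read through its interval and not as proof of no added value.

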2. STUDY OBJECTIVES

- **Primary research objective** is to investigate the correlation and agreement between the intraocular pressure peaks detected during the water drinking test and the standard phasing test.

Secondary research objective is to correlate the IOPs obtained with both tests and prognostic outcome of the patients enrolled in the study to see whether these methods have predictive value for glaucoma progression. We will also measure autonomic nervous system activation (pupil size, heart rate and postural BP) during the test to investigate one possible mechanism behind it.

Lay summary

Raised intraocular pressure (IOP) is the main risk factor for the development and progression of glaucoma. The mDTC is a test that consists of four to five eye pressure measurements taken throughout office hours to check for rises in pressure that may be missed during their clinic appointment. To better try to assess the IOP peaks in a more time-efficient way, the water-drinking test has been developed. This involves the patient drinking a weight-adjusted volume of water within 5 minutes which has the effect of testing the ability to cope with increased demand for fluid to leave the eye. It is unclear as to the physiological mechanism by which this occurs. In this study we aim to compare the eye pressure measurements with both tests, and to see if either have any bearing on whether the patient's disease is getting worse. We also aim to show the changes in blood pressure and heart rate throughout the test.

